A subject may be discharged after completion of assessments at 6 hours post treatment, if deemed medically stable in the investigator's clinical judgment and, if applicable, the subject's HAE symptoms have resolved (the subject's investigator-rated symptom score must be zero, denoting the absence of symptoms). If HAE symptoms have not completely resolved at 6 hours (ie, the investigator-rated symptom score is >0), the subject shall remain in the hospital/study center for at least 8 hours after icatibant administration for further evaluation.

Telephone follow-up will occur at both 24 and 48 hours after treatment.

Subjects will return to the hospital/study center for scheduled assessments on Day 8 and for a follow-up visit on Day 90.

The investigator will schedule a telephone contact approximately 6 months after Day 1 of initial icatibant-treatment to obtain specific updates concerning pubertal changes/milestones.

Subsequent Icatibant-treated Attacks

After having received initial treatment with icatibant, either during or in the absence of an attack, at least 10 pubertal/postpubertal subjects who subsequently experience an acute HAE attack may continue to receive treatment with icatibant as a single SC administration per attack for a total of 3 eligible icatibant treatments. Further treatment with icatibant is contingent upon presentation of an acute cutaneous, abdominal, or laryngeal attack of HAE at least 3 days after prior treatment.

For subsequent attacks, study drug may be administered by study site personnel at the hospital/study center or by qualified home healthcare personnel at the subject's home. Alternatively, a parent/legal guardian/caregiver will be allowed to administer or the subject (under the supervision of a parent/legal guardian/caregiver) will be allowed to self-administer the investigational product after having received appropriate training. For all subsequent laryngeal attacks, subjects should be advised to seek medical attention in an appropriate healthcare facility immediately following treatment with icatibant.

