4.1.3.1 Initial Treatment

In previously screened, eligible subjects who present with an attack of acute HAE, baseline clinical assessments for PK, safety, and efficacy will be performed on Day 1 at pretreatment. The initial severity and type of attack (ie, cutaneous, abdominal, or laryngeal) will be determined by the investigator. The investigator will complete baseline assessments at pretreatment of the symptoms of the acute HAE attack (including a separate assessment of HAE-related pain in subjects younger than 4 years of age), and adherence to inclusion/exclusion criteria will be reconfirmed. Subjects who are 4 years of age or older will perform a self-assessment of HAE-related pain. Other baseline assessments performed at pretreatment will include physical examination, pubertal status determination (only for those subjects classified as prepubertal at screening), height and weight, vital signs, collection of samples for clinical laboratory tests (serum chemistry [including liver function tests], hematology, urinalysis), urine pregnancy test for pubertal/postpubertal females, baseline PK and immunogenicity assessments, and baseline measurement of reproductive hormones (FSH, LH, estradiol, and progesterone in females and FSH, LH, and testosterone in males).

On Day 1, subjects will be administered a single dose of icatibant as an abdominal SC injection within 12 hours after the onset of the acute attack. The time of investigational product administration on Day 1 will be designated as Time 0. All post-treatment assessments will be calculated from the time of investigational product administration. PK, safety, and efficacy assessments will be performed on Day 1 after treatment at the time points indicated in the study schedules of events ([Appendix 1](#), [Appendix 2](#)). These assessments will consist of physical examination, vital signs, ECG, clinical laboratory tests (serum chemistry [including liver function tests], hematology, urinalysis), injection site reactions, and measurement of reproductive hormones (FSH, LH, estradiol, and progesterone in females and FSH, LH, and testosterone in males) in all subjects. The investigator will complete assessments of symptoms of the acute attack of HAE for all subjects (including a separate assessment of HAE-related pain in subjects younger than 4 years of age). Subject who are 4 years of age or older will also complete a self-assessment of HAE-related pain.

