7.11 Efficacy Assessments

7.11.1 Symptom Score

7.11.1.1 Investigator Symptom Score

For subjects treated at the hospital/study center, the investigator will use a symptom score to assess the severities of symptoms of acute cutaneous, abdominal, and laryngeal attacks of HAE using the following 5-point scale. Symptom scores will be recorded on Day 1 at pretreatment and at predetermined time points after treatment. Results will be recorded in the CRF.

Investigator-rated Symptom Score

- 0 = none; absence of symptoms
- 1 = mild (no to mild interference with daily activities)
- 2 = moderate (moderate interference with daily activities)
- 3 = severe (severe interference with daily activities)
- 4 = very severe (very severe interference with daily activities)

For attacks classified as cutaneous and/or abdominal, investigator-rated symptom scores will be collected for 8 symptoms: abdominal tenderness, nausea, vomiting, diarrhea, skin pain, erythema, skin irritation, and skin swelling.

For attacks classified as laryngeal, investigator-assessed symptom scores will be collected for 13 symptoms: abdominal tenderness, nausea, vomiting, diarrhea, skin pain, erythema, skin irritation, skin swelling, dysphagia, voice change, breathing difficulties, stridor, and asphyxia.

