7.11.1.2 Home Healthcare Provider or Parent/Legal Guardian/Caregiver Symptom Score

The home healthcare provider or parent/legal guardian/caregiver, after having received appropriate training, will assess the severities of symptoms of acute cutaneous, abdominal, and laryngeal attacks of HAE using the 5-point scale provided in Section 7.11.1.1. Symptom scores will be recorded on Day 1 at pretreatment and at predetermined time points after treatment. Results will be recorded in the CRF.

For attacks classified as cutaneous and/or abdominal, the home healthcare provider or parent/legal guardian/caregiver-rated symptom scores will be collected for 8 symptoms: abdominal tenderness, nausea, vomiting, diarrhea, skin pain, erythema, skin irritation, and skin swelling.

For attacks classified as laryngeal, the home healthcare provider or parent/legal guardian/caregiver-assessed symptom scores will be collected for 13 symptoms: abdominal

tenderness, nausea, vomiting, diarrhea, skin pain, erythema, skin irritation, skin swelling, dysphagia, voice change, breathing difficulties, stridor, and asphyxia.

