7.17 Adverse Events Assessments

7.17.1 Definitions of Adverse Events and Serious Adverse Events

7.17.1.1 Adverse Event

An AE is any noxious, pathologic, or unintended change in anatomical, physiologic, or metabolic function as indicated by physical signs, symptoms, or laboratory changes occurring in a clinical study, whether or not considered investigational product related. This includes an exacerbation of a pre-existing condition. However, any exacerbation or worsening of symptoms of an acute HAE attack treated with icatibant is considered a result of the underlying disease and will not be considered an AE (unless meeting the criteria for a serious adverse event (SAE), see Section 7.17.1.2).

Adverse events include:

- Worsening (change in nature, severity, or frequency) of conditions present at the onset of the study (with the exception of HAE).
- Intercurrent illnesses.
- Drug interactions.
- Events related to or possibly related to concomitant medications.
- Clinically significant abnormal laboratory values (this includes significant shifts from baseline within the range of normal that the investigator considers to be clinically important).
- Clinically significant abnormalities in physical examination, vital signs, and weight.

The investigator must record all AEs in the CRF, regardless of the severity or relationship to investigational product. The investigator should treat subjects with AEs appropriately and observe them at suitable intervals until the events stabilize or resolve. Adverse events may be discovered through observation or examination of the subject, questioning of the subject, complaint by the subject, or by abnormal clinical laboratory values.

In addition, AEs may also include laboratory values that become clinically significantly out of range. In the event of an out-of-range value, the laboratory test should be repeated until it returns to normal or stabilizes, or can be medically explained, and the subject's safety is not at risk.

Additional illnesses present at the time when informed consent is given until the time of treatment are regarded as concomitant illnesses and will be documented on the medical history page of the CRF. Illnesses first occurring or detected on or after treatment, and worsening of a

concomitant illness during the study, are to be regarded as AEs and must be documented as such in the CRF.

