#### 7.8.1 Investigator Symptom Score

The primary efficacy endpoint is the time to onset of symptom relief measured using the investigator-reported symptom score. Eight symptoms will be assessed for abdominal and cutaneous attacks, and 13 symptoms will be assessed for laryngeal attacks. Time to onset of symptom relief is defined as the duration of time in hours from study drug administration to the earliest time post-treatment at which there is at least a 20% improvement in the composite (or average) post-treatment symptom score with no worsening of any single component score.

Subjects not achieving the onset of symptom relief will be censored at the time of their last symptom assessment. Time to onset of symptom relief will be summarized using the Kaplan-Meier method.

An alternative efficacy endpoint is the time to minimum symptoms measured using the investigator-reported symptom score. It is defined as the earliest time post-treatment when all symptoms are either mild or absent. Subjects not achieving the minimum symptom criteria will be censored at the time of their last symptom assessment. Time to minimum symptoms will be summarized using the Kaplan-Meier method. Subjects with all symptoms as mild or absent at pretreatment will be excluded from this analysis.

The composite investigator-reported symptom score and the change from pre-treatment in the composite investigator-reported symptom score will be summarized by study time-point. Furthermore, the symptom scores associated with individual symptoms will be summarized by study time-point. The mean composite investigator-assessed symptom score will be plotted by study time-point by pubertal status stratification group.

For individual investigator-reported symptom scores, a shift table from baseline will be presented for each post-treatment time point. The analysis will be repeated to assess shift in the individual symptom scores from the 2 hour time-point.

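### The five laryngeal items are scored only in attacks classified as laryngeal, so new laryngeal symptoms after dosing in a cutaneous or abdominal attack can go unseen by the relief and minimal-symptom rules

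*Protocol*

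**What the plan says.** Two item sets are used, chosen by attack type. Protocol 7.11.1.1 gives the short form: "For attacks classified as cutaneous and/or abdominal, investigator-rated symptom scores will be collected for 8 symptoms". The same section gives the long form: "For attacks classified as laryngeal, investigator-assessed symptom scores will be collected for 13 symptoms". The long form is the same eight symptoms plus dysphagia, voice change, breathing difficulties, stridor and asphyxia. Protocol 7.11.1.2 repeats the split for home healthcare providers and caregivers, and SAP 7.8.1 repeats it for the analysis: "Eight symptoms will be assessed for abdominal and cutaneous attacks, and 13 symptoms will be assessed for laryngeal attacks".

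For the initial treatment, Protocol 4.1.3.1 sets the type at the Day 1 pretreatment assessment: "The initial severity and type of attack (ie, cutaneous, abdominal, or laryngeal) will be determined by the investigator". Neither document has a rule for laryngeal involvement that appears later.

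Three endpoints depend on symptom intensity:

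- Onset of relief is the "earliest time post-treatment at which there is at least a 20% improvement in the composite (or average) post-treatment symptom score", provided no scored component is worse (SAP 7.8.1).
- Minimal symptoms is the first time all symptoms on the investigator score are mild or absent.
- Worsened intensity between 2 and 4 hours is listed in Protocol 3.2 and SAP 5 without a derivation. The nearest analysis is the shift table of individual scores from 2 hours.

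Protocol 7.17.1.1 treats symptoms within 48 hours of onset as part of the treated attack. It says "any exacerbation or worsening of symptoms of an acute HAE attack treated with icatibant is considered a result of the underlying disease", so worsening is not an adverse event unless serious. Clinically relevant worsening goes on a separate CRF page.

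**The concern.** An item that is not collected cannot fail a rule. The no-worsening condition and the all-symptoms condition are there to stop an attack being called a success while part of it is getting worse. On the 8-item form they do not cover the airway. Site of involvement does not explain this, because a purely cutaneous attack is already scored on four abdominal items.

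At stake is the credibility of time to onset of relief, which SAP 7.8.1 calls the primary efficacy endpoint, and of time to minimal symptoms. Protocol 1.1 notes that asphyxia may develop faster in children than in adults, so a reader would expect this kind of progression to count against relief. No sensitivity analysis is planned (SAP 9.7).

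A second, separate issue is scale. The composite is an average over 8 items in some attacks and 13 in others, and SAP 7.8.1 summarises and plots these averages together.

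**Working it through.** The plan states no figure on this point, so there is nothing to reproduce. The inputs are the item lists (8 and 13), the 20% threshold with its no-worsening condition, and the mild-or-absent rule. The score profiles below are assumptions chosen for illustration.

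**Direction.** Let B and P be the totals of the eight items before and after dosing, and L the total of new laryngeal scores, with laryngeal baseline 0.

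- Improvement on 8 items: (B − P)/B.
- Improvement on 13 items: (B − P − L)/B.

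The second is never larger, and the 13-item form only adds conditions. A 13-item success can therefore never come earlier than the 8-item one.

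**Relief.** Baseline: skin swelling 3, skin pain 2 (B = 5). At 1 hour: swelling 2, pain 2 (P = 4), with new dysphagia 2 and voice change 2 (L = 4).

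- 8 items: 5/8 = 0.625 to 4/8 = 0.500. Improvement is 1/5 = 20% and no item is worse, so relief is counted.
- 13 items: 5/13 = 0.385 to 8/13 = 0.615. This is 3/5 = 60% worse with two items worse, so no relief.

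**Minimal symptoms.** Baseline: skin pain 2, erythema 1, swelling 3 (B = 6). After dosing: pain 1, swelling 1 (P = 2), with new dysphagia 2, voice change 2, breathing difficulties 3 and stridor 2 (L = 9).

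- 8 items: 0.75 to 0.25, a 67% improvement. Both relief and minimal symptoms are met.
- 13 items: 6/13 = 0.462 to 11/13 = 0.846, 83% worse. Neither is met.

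If the new symptoms were only mild (dysphagia 1, voice change 1), relief would still fail on 13 items but minimal symptoms would be met.

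**2 to 4 hours.** With the eight items unchanged and new voice change 2 and breathing difficulties 2, the 8-item shift table shows no worsening. A 13-item table would.

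**Size.** The documents give no rate of laryngeal spread. If each attack carried an independent chance q of it, the chance of at least one case in n attacks is 1 − (1 − q)^n:

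| Assumed q | n = 10 | n = 20 |
|---|---|---|
| 1% | 10% | 18% |
| 3% | 26% | 46% |
| 5% | 40% | 64% |
| 10% | 65% | 88% |

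One subject is 1/10 = 10 points of a proportion in a pubertal group of 10, or 1/20 = 5 points overall. This applies to the 2-to-4-hour proportion only.

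**Pooling.** A total of 8 gives 8/8 = 1.00 or 8/13 = 0.62, 38% lower for the same burden.

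**If a site switches forms by itself.** The five baselines are then missing. Protocol 10.10, read as referring to missing pretreatment scores, assigns zero. SAP 9.2.1 and 10.2.9 assign the mean of the other items. Take the second profile with only two new laryngeal items at 2. The composite goes 0.462 to 0.462 (0%) under the first rule and 0.75 to 0.462 (38% better) under the second.

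**The case against.** Several points against a stronger reading stand.

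- A reader might infer that the classification is locked and the laryngeal items can never be rated. No passage says so: Protocol 4.1.3.1 speaks of the initial type, for the initial treatment, and the CRF is not available. What stands is that no rule for a change is written, and an improvised switch meets two conflicting imputation rules.
- A reader might infer that any later spread turns a relieved attack into a false success. It does not. Onset is the earliest qualifying time and need not be sustained. Protocol 1.2.2 already reports a median of 1.0 hour (95% CI 1.0 to 1.1). Relief changes only if the spread is present when the 8-item score first qualifies.
- A reader might apply 10 percentage points to relief. That endpoint is summarised by Kaplan-Meier percentiles, and one subject in ten need not move a median.
- A reader might conclude that the bias always favours the drug. That is true of unscored spread but not of pooling, which also shrinks absolute change in laryngeal attacks.
- The 2-to-4-hour endpoint has no derivation, so its blindness is shown only for the shift table.
- Serious adverse events, rescue medication and investigator-noted overall improvement can reveal spread. None of them overrides relief or minimal symptoms. The rescue time-to-event analysis is censored at relief, so a falsely early relief also hides later rescue there, although the rescue medication tables would still show it.
- Efficacy is secondary and descriptive, and Protocol 1.1 calls laryngeal attacks infrequent.

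**Conclusion.** The point holds in this limited form. Followed as written, the documents let a cutaneous or abdominal attack with new laryngeal symptoms be counted as relieved, or as having minimal symptoms, at the time the 8-item score first qualifies. The shift table from 2 hours would not show the spread either. For this misclassification the error can run only in the drug's favour, assuming no laryngeal symptoms at baseline. Its frequency is unknown, probably few subjects are affected, and the medians may not change. It does not touch the study's primary endpoints, which are pharmacokinetics and safety.

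The pooling of 8-item and 13-item averages is a separate scale defect with no fixed direction.

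The discharge wording in Protocol 4.1.2 and 8.3.2 relies on the same score: "the subject's investigator-rated symptom score must be zero, denoting the absence of symptoms". On the 8-item form a zero says nothing about five listed attack symptoms. A reader might infer that discharge rests on that zero alone. It does not, because the investigator must also judge the subject medically stable.

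**What to change.** 1. In SAP 7.8.1, add a rule for new laryngeal symptoms recorded on any CRF page, including the worsening page of Protocol 7.17.1.1. The attack does not meet onset of relief at any time point while they are present, or minimal symptoms while they are more than mild. It counts as worsened if they arise or increase between 2 and 4 hours. Relief reached before the spread is kept. State a convention for entries without a time or severity, since the page's content is not visible here.
2. Derive the 2-to-4-hour worsening endpoint explicitly, including new laryngeal symptoms. Say what is used when no 4-hour score exists, which Protocol Appendix 3 permits in subsequent attacks if symptoms are mild or absent at 2 hours.
3. Present composite means and plots separately for 8-item and 13-item attacks, or use a common item set.
4. For remaining subsequent attacks, score all 13 items at pretreatment and at every time point, and also report the 8-item result. Initial treatment is complete (Protocol 1.2.2), so this cannot reach exposure 1.
5. Reconcile the statement that a zero score denotes absence of symptoms with the item list used. No clinical rule is proposed.

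Items 1 to 3 cost SAP wording, a check of existing CRF pages and a few split tables. Item 4 costs five more ratings per scoring, a form update and an item set that differs from exposure 1. The 8-item result preserves comparability. Percent improvement is unchanged by item 4 when there are no laryngeal symptoms and no baseline item is missing. With one baseline item missing, the others totalling 5, and a later total of 4, SAP imputation gives 30% on 8 items (5/7 = 0.714 to 4/8 = 0.500) and 26% on 13 (5/12 = 0.417 to 4/13 = 0.308).

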7.11.1.2 Home Healthcare Provider or Parent/Legal Guardian/Caregiver Symptom Score

The home healthcare provider or parent/legal guardian/caregiver, after having received appropriate training, will assess the severities of symptoms of acute cutaneous, abdominal, and laryngeal attacks of HAE using the 5-point scale provided in Section 7.11.1.1. Symptom scores will be recorded on Day 1 at pretreatment and at predetermined time points after treatment. Results will be recorded in the CRF.

For attacks classified as cutaneous and/or abdominal, the home healthcare provider or parent/legal guardian/caregiver-rated symptom scores will be collected for 8 symptoms: abdominal tenderness, nausea, vomiting, diarrhea, skin pain, erythema, skin irritation, and skin swelling.

For attacks classified as laryngeal, the home healthcare provider or parent/legal guardian/caregiver-assessed symptom scores will be collected for 13 symptoms: abdominal

tenderness, nausea, vomiting, diarrhea, skin pain, erythema, skin irritation, skin swelling, dysphagia, voice change, breathing difficulties, stridor, and asphyxia.

7.11.2 Subject Self-assessment of Pain

Subjects who are at least 4 years of age will self-assess HAE-related pain using the FPS-R. A copy of the FPS-R is provided in [Appendix 5](#).

FPS-R self-assessment data will be recorded in a diary. Subjects will record self-assessments on Day 1 at pretreatment and at predetermined time points after treatment. Subjects will return the diary to the hospital/study center at the scheduled visit on Day 8.

Subjects will receive detailed instruction on when and how to use the diary from the investigator and/or clinical site personnel.

7.11.3 Investigator Assessment of Pain

Subjects who are below 4 years of age will undergo investigator assessment of HAE-related pain (cutaneous, abdominal, and laryngeal) using the FLACC compartmental pain scale. A copy of the FLACC scale is provided in [Appendix 6](#).

7.11.4 Initial Symptom Relief

7.11.4.1 Investigator-assessed Initial Symptom Relief

For subjects treated at the hospital/study center, the investigator will be asked to record the date and time when overall subject improvement was first noted and mark the date and time accordingly in the CRF.

7.11.4.2 Home Healthcare Provider and Parent/Legal Guardian/Caregiver Initial Symptom Relief

The home healthcare provider or parent/legal guardian/caregiver, after having received appropriate training, will be asked to record the date and time when overall subject improvement was first noted and record the date and time.

